Study protocol for Randomised Double Blinded Controlled Trial with a longitudinal design monitoring effect of COMprehensive Intensive REhabilitation Program after STROKE (COMIRESTROKE)

NCT05323916

22.4.2022

1. Introduction

Ischemic stroke is one of the leading causes of neurological dysfunction, the most common being motor disability which negatively impacts quality of life and active participation (1, 2). There is evidence supporting the positive influence of rehabilitation in well-coordinated multidisciplinary stroke units (3) where physiotherapy (PT) plays an indisputable role in impairment reduction, activity independence, social participation and quality-of-life improvement (4). On the other hand, clear evidence concerning the effectiveness of different PT approaches as part of rehabilitation is still lacking. Several large intervention trials have reported that participants' motor performance increased. Nevertheless, this was enhanced to a similar extent for both the intervention and control groups in most trials (5). Small beneficial differences between groups could be caused by a non-systematic/accidental indication of PT methods in rehabilitation processes. Research from other areas also suggests that between-group differences in improvement may be found on an item level of multi-item measurements even in cases when they are not observed on the total scores, and thus, a more detailed item-level analysis may provide an important insight (6, 7).

Many PT techniques have been developed to facilitate the recovery of motor disability in patients after stroke (3, 8-10). All are related to neural plasticity via the development of new neuronal interconnections, acquiring new functions, and compensating for impairment (11), but they explain little in relation to the mechanisms underlying motor recovery heterogeneity. Physical activity training acts as an acute stress that enhances neurobiological processes such as activity-dependent plasticity, learning and memory. Motor/skill acquisitions and technology based PTs systematically train damaged function by the repetition of new and complex movements, which induces a substantial cortical network reorganization closely related topographically to the trained movement which leads to synaptogenesis (12). Neuroproprioceptive "facilitation, inhibition" (neurofacilitation) PT enhances the effectiveness of the synaptic connections among neurons forming functional networks, which leads to the evocation of movement by some otherwise weak and insufficient stimuli. A suitable combination of afferent stimuli modulates interneuronal systems, repeatedly activates motor programs at the subcortical level, and as such induces adaptive and plastic processes of the CNS (13). We are convinced that to prevent maladaptive plasticity, and maximize functional gain in patients with stroke, individualized therapeutic goals, should be considered. The ICF model proposes a comprehensive, biopsychosocial approach to patients, setting personalised goals based not only on diagnosis but also on the patients' functional status and activities. It has been recommended by the World Health Organisation (WHO) (14), and was globally agreed-on as a conceptual framework and common language to document and code functional status information (15, 16). However, to date the basis of such a personalised approach to ischemic stroke (IS) therapy has not been clearly clarified, described and confirmed yet. This clinical trial will address this gap in IS rehabilitation as follows using a

three-pronged approach to the COMprehensive Intensive REhabilitation Program after STROKE (COMIRESTROKE): **COMIRESTROKE** – **ICF**, the mostly individualized approach implementing the International Classification of Functioning, Disability and Health (ICF) model with aim to improve an individual's recovery (rather than impairment) through effective management of care (14); **COMIRESTROKE** – **TECH**, approach implementing technology-based PT" and **COMIRESTROKE** – **NEFI**, approach implementing neuroproprioceptive "facilitation and inhibition" PT.

There is very limited evidence to guide judgements regarding the rehabilitation potential following stroke (17-20). Research shows that some clinical features such as the level of consciousness, severity of hemiplegia, incontinence, dysphagia and dysphasia (21) or disease severity (22, 23) may be considered as indicators as to whether the rehabilitation process could be effective. However, confusion between predicting natural unassisted recovery and predicting responsiveness to targeted rehabilitation still remains (17). Moreover, prediction models of rehabilitation potential have never been fully and properly prospectively tested. The models considered by Prabhakaran et al., 2008 were only able to explain 47% of the variance in recovery after stroke with 53% of the variance remaining unaccounted (24). Nowadays focus shifted from the determination of rehabilitation potential to identifying clear indicators of effective rehabilitation including molecular biological readouts (25). This is reason why a wide range of patient characteristics will be collected. We consider, the patients' subjective feelings about how they have improved to be the most important aspect. Therefore, the Goal Attainment scale (GAS) together with the Patient-reported Outcomes Measurement Information System (PROMIS) Global Health, and the World Health Organization Disability Assessment Schedule (WHODAS 2.0) were chosen as primary outcomes. As secondary outcomes, measurements will be taken of motor, cognitive, psychological, speech and swallowing functions as well as functional independence.

Moreover, focus will be placed on the identification of novel biological molecules reflective of effective rehabilitation by molecular assessment. Long non-coding RNA (lncRNA) are defined as RNA transcripts >200 nucleotides with limited coding potential (26). They have been classified into anti-sense, intronic, large intergenic, promoter associated and UTRassociated lncRNAs (27). They are involved in vital cellular regulation (28) including genomic imprinting (29), epigenetic chromatin modification (30), transcriptional interference (31) and nuclear export (32). Importantly, IncRNAs determine nervous system development (33). A majority of lncRNA display specific expression within neuroanatomical regions (34). Many of these lncRNAs display genomic localizations in close proximity to known neurodevelopmental regulators (35). This has led to the general hypothesis that the expanded diversity in lncRNAs is pivotal to the higher order cognitive ability of humans. Long noncoding RNAs as promising therapeutics biomarkers in IS: LncRNAs regulate key factors involved in ischemic/reperfusion injury eg. calcium overload (Chen et al 2019). Excessive calcium accumulation results in the activation of calcium/calmodulin-dependent protein kinase II (CaMKII), a family of serine/threonine kinases involved in IS pathogenesis (36). CaMKII is controlled by lncRNA C2dat1. Elevated levels of lncRNA C2dat1 have been identified in both in vitro and in vivo models of IS (36). Studies showed that IS injury leads to increased glutamate release activating N-methyl-D-aspartate (NMDA) receptors which initiate cellular apoptosis (37). Overexpression of lncRNA GAS5 increased the apoptotic rate in neurons with its administration resulting in a greater area of cerebral infarction in animal models (38). It has been suggested that inhibition of the lncRNA GAS5 could potentially reduce apoptosis and infarct size in IS leading to improved neurological functioning. Evidence has pointed to IncRNA moderation of autophagy, angiogenesis and oxidative stress caused by IS. Exploring IncRNAs involved in such processes will assist in understanding the recovery networks induced by IS rehabilitation approaches.

2. Participants and methods

2.1. Clinical trial design

This will be a Four-Arm Parallel-Group Randomised Double Blinded Controlled Trial with a longitudinal design. Patients who fulfilled inclusion criteria will be randomly assigned to one of the four research groups (Group 1, 2, 3 or 4). Three groups will undergo an inpatient COMIRESTROKE (4 hours/day for 3 weeks). Group 1 (COMIRESTROKE – ICF) will undergo individualised rehabilitation therapy embodying the ICF system as a therapeutic tool, where current needs and wishes of the person after IS are integrated into an interdisciplinary team rehabilitation programme management. Group 2 and 3 will undergo a standard comprehensive intensive rehabilitation program three hours per day (39) plus one hour of specific PT (an individual neuroproprioceptive "facilitation inhibition" for Group 2, a technology-based training for Group 3). Group 4 will undergo standard care and will serve as comparative one to the intensified intervention groups.

Participants will be examined four times (Figure 1). At the beginning and after three weeks of hospitalization (both primary, secondary outcomes and a blood draw will be obtained for total RNA extraction, cDNA synthesis and real-time QPCR assessment of lncRNA candidates previously identified as potential therapeutic influencers in ischemic stroke), and then three months and one year after the end of the program (primary outcomes only).

Figure 1: Design of the study

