2.3. A detailed description of four groups

Three groups in intervention cohorts will receive the same length of rehabilitation, i.e., 4 hours per day. Therapists in each group will be maximally helpful and will adopt a schedule for each patient to complete all the sessions. The treatment in each session will be led in person by well-educated, experienced therapists specially trained in each method. The treatment will be modified according to the patient's status and reaction to the therapy. Physical load during all therapies will be perceived maximally as a moderate level of intensity [12 - 14 on the Borg Scale (45)]. Information about the treatment will be recorded using codes of Public Health Insurance, Czech Republic (codes correspond to The Current Procedural Terminology code set system).

Group 1: COMprehensive Intensive REhabilitation Program after STROKE implementing the ICF concept (COMIRESTROKE – ICF)

This interventional arm suits the purposes of setting individual goals of the therapy which take account of the given situation of the rehabilitated person (46-48). The ICF system establishes a common health language to articulate human functioning across the lifespan and from individual to population health settings system (49, 50). On the individual level, functioning is considered as an interaction between a health condition and the contextual factors facilitating or acting as a barrier for functioning (51). Focusing on patient's quality of life and participation domain of the ICF applies a paradigm shift in neurorehabilitation research design (52). Engagement in valued activities was found to be significantly associated with subsequent improvement in emotional well-being (53).

Patients randomized to the GROUP 1 will undergo a multidimensional assessment, a functional profile will be created and the individual goals and intervention proposed and defined throughout the ICF framework. Clinical application can be rather arduous (54) and sharing of the feasibility experience is highly valued. This study arm design follows recommendations and

experience with implementation of the ICF model into clinical practice in rehabilitation in people after stroke (55).

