Limiting the burden of iterative processing the proposed battery of clinical examinations, questionnaires surveys and filling out the ICF core set documentation which is then used to compile "ICF Categorical Profile", this study proposes a direct linking of some clinical test results to the codes included in the Comprehensive ICF core set for stroke used (56). Linking of normal-range clinical examination results may ease the procedure. Linking will take place regarding specified items from the test battery: WHODAS 2.0 (57) NIHSS, mRS, MoCA (58), MAL (59), FIM, BBS (60), TUG, NHPT, ARAT, GSS, 3F test, MAST. Overlapping items will be further discussed.

The clinical assessment involves the following three steps: 1) description of patient's problems and resource; 2) setting of mutually agreed goals, based on the functional profile; 3) and determination of intervention targets. The interdisciplinary team together with the patient will use the functional profile to define in detail the overall goal and sub-goals, and to determine specific therapeutic interventions to achieve them (42). Participants in this group will undergo four hours of treatment per day (the same time as in the remaining two cohorts), but the time spent with each specialist will depend on the individually set goals. The "ICF Intervention Table" will be used to monitor and evaluate the work during individual targeted interventions and will also serves as a means of communication between the members of the interdisciplinary team. The team will meet weekly to provide feedback, evaluate the fulfilment of the set goals and to adjust therapeutic procedures so that the goals of the therapy are best met.

After the end of the intensive complex inpatient program COMIRESTROKE – ICF, as the continuum of care, participants will be referred and to a short-term outpatient rehabilitation programme.

Group 2 and 3

Participants will undergo COMprehensive Intensive REhabilitation Program after STROKE routinely offered at the Department of Rheumatology and Rehabilitation, Third Faculty of Medicine, Charles University and Thomayer University Hospital (39) three hours per day. In the program, the multidisciplinary team of practitioners from different clinical fields (physiotherapy, occupational therapy, clinical speech therapy and psychology) will be led by a medical doctor, a specialist in rehabilitation and physical medicine. Efforts of the different team members are parallel and discipline oriented.

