In addition, participants in these two groups will undergo one hour of physiotherapy per day. **Group 2:** COMprehensive Intensive REhabilitation Program after STROKE implementing technology-based physical PT (COMIRESTROKE – TECH) Participants will receive a technology-based PT that follows the principles of sensorimotor learning, i.e. repeated specific and targeted functions in different environments / conditions in order to strengthen the memory footprint and initiate structural changes in the CNS. According to the indication, participants will be offered one of the robotic systems using an exoskeleton (Gloreha, Erigo and Meditutor) or a therapy using a virtual environment (61, 62).

Group 3: COMprehensive Intensive REhabilitation Program after STROKE implementing neuroproprioceptive "facilitation and inhibition" physiotherapy (COMIRESTROKE – NEFI). Participants will receive an individual neuroproprioceptive "facilitation, inhibition" PT (Vojta reflex locomotion, Bobath concept), where appropriate stimuli in a suitable time sequence are combined with the aim to maintain optimal motor pathway function and ability control (63, 64). After finishing this intensive complex inpatient program COMIRESTROKE, participants will undergo standard/not directed treatment offered by the Czech Health Care system. Information

as to the health and social care the rehabilitant received after hospitalisation will be collected by phone call.

Group 4: A comparative group will undergo standardly provided care at department of neurology including face to face physiotherapy (bed mobility, transfers, gait, therapeutic exercises, positioning, education).

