2.4. Pre- and post-intervention assessments

Once an informed consent is obtained prior to randomisation; participants will be referred to study examiners - a Physical Medicine and Rehabilitation physician, a neurologist, a physical therapist, an occupational therapist and a psychologist, who will not know the treatment group of the patient. They will administer baseline testing during the 2nd and 3rd day after admission to the department (Pre-assessment). The Post-assessment 1 will be done at the end of the three-week inpatient intensive comprehensive rehabilitation (during the last two days of hospitalization). Follow-up assessments will take place 3 and 12 months after the admission, respectively, by a telephone interview and hospital visit for blood draw. The aim is to be assessed only by one examiner, in case of more examiners, inter-rater reliability will be assessed (Table 2).

test	abbreviation	Inclusion and exclusion criteria	Examination No			
			1	2	3	4
			baseli	+3	+3	+ 1
			ne	weeks	month s	year
Neurologist						
Demographic and anamnestic data (age, after first ischemic stroke, days after the stroke) Demographic and anamnestic data (weight and height, cardiovascular risk factors, Bamford classification, medication)			x			
Modified Rankin Scale	mRS	Х		х		
Pre-Stroke Modified Rankin Score	pre-stroke mRS	Х				
Historic Stroke Motor Severity Score	HSSS	Х				
National Institute of Health Stroke Scale	NIHSS	Х				
Psychologist*						
Montreal Cognitive Assessment	MoCA		Х			
Amnesia Light and Brief Assessment	ALBA		х	х		
NEO-Five Factor Inventory	NEO - FFI		х			
Patient-reported Outcomes Measurement Information System Global Health	PROMIS		х	х	х	х
the World Health Organization Disability Assessment Schedule	WHODAS		Х	Х	Х	Х

Table 2: Timing and distribution of examination in the team

the Goal Attainment scale	GAS				
Picture naming and immediate recall	PICNIR	х	х		
Neuro - QOL depression		х	х		
physical therapist					
Hand Dynamometer		Х	Х		
postural tremor		х	х		
Action Research Arm Test*	ARAT	х	х		
Motor Activity Log*	MAL	х	x		
Timed Up and Go*	TUG	х	x		
Berg Balance Scale*	BBS	х	x		
The 10 Metre Walk Test*		x	х		
The 6 Minute Walk Test*		x	х		
Functional Independence Measure*	FIM	х	х		
Laterality index	LI	х			
Nine Hole Peg Test		х	х		
speech therapist*					
The Gugging Swallowing Screen	GSS	Х	х		
The 3F Test – Dysarthric Profile	3F test	х	х	-	
Dysan		х	х		
The Mississippi Aphasia Screening	MAST	х	х		
Test					
Image Naming Test	INT	Х	X		

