2.5. Outcomes and measures

2.5.1. Primary Outcomes

- PROMIS Global Health is a 10-item scale which asks the patient to assess (self-report) their physical, mental and social health in the past 7 days (72, 73).
- WHODAS 2.0 is a generic assessment instrument developed by WHO to provide a standardized method for measuring health and disability. It is grounded in the conceptual framework of the ICF and integrates an individual's level of functioning in major life domains and directly corresponds with ICF's "activity and participation" dimensions. The 36-item version will be used. Higher score means higher disability (74).
- GAS is an individualized outcome measure involving goal selection and goal scaling that is standardized in order to calculate the extent to which patient's goals are met. Each goal is rated on 5-point scale (-2 much less than expected, 0 achieved the expected level, 2 much more than expected (75, 76).

Three types goals will be established:

A. Overarching long-term goal (Global Goal, G) that reflects a desired improvement on the level of participation: usually restoration of previous life including remunerative employment, sport and leisure activities (interview by call at 3 and 12 months follow up).

B. Mid-term goal (Program Goal, P) that reflects improvement mainly in the domain of activities and participations achievable by the rehabilitation program: restoration of self-care, (almost) independence in daily living etc. (interview by call at 3 months follow up)

C. Three Short-term goals (Cycle Goals C1, C2, C3) mainly in the domain of functioning and activities. Usually specific, most problematic components of the Program Goal (evaluated by the rehabilitation team together with the rehabilitant).

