2.5.3. Other Pre-specified Outcome Measures - molecular biological readouts of rehabilitation

Blood will be taken for total RNA extraction, cDNA synthesis and real-time QPCR assessment of lncRNA candidates previously identified as potential therapeutic influencers in ischemic stroke. Whole blood will be collected from fasting patients for RNA analysis. A RiboPureTM-Blood Kit (cat# AM1928, ThermoFisher Scientific) will be used for isolating high-quality RNA directly from whole blood. This kit contains an RNA*later*® Solution (cat.# AM7020, ThermoFisher Scientific) that protects RNA and is designed to eliminate the need to process samples as soon as they are harvested. RNA*later*® Solution also "freezes" the gene expression profile of the cells. Treated samples can be safely stored at ambient temperature for extended periods of time (up to three days or more). Blood samples stored in RNA*later*® Solution yield RNA of comparable quality to blood samples processed directly according to the commercial website. Expected average yields of total RNA will be between 2–4 µg/0.5 mL of whole blood. Total RNA will be reverse transcribed into cDNA. Human lncRNA and internal endogenous gene (eg. *GAPDH*) expression will be quantified using RNA extracted from blinded samples (ie. concealment of group allocation) to eliminate bias.

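### The trial is called double blinded, but only examiners and laboratory samples are masked, so group differences on the patient- and team-dependent primary outcomes are not double-blind evidence

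*Combined protocol and SAP*

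**What the plan says.** The title and section 2.1 use the double-blind label: "This will be a Four-Arm Parallel-Group Randomised Double Blinded Controlled Trial with a longitudinal design". Neither names the two blinded parties.

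Masking is described in two places. Section 2.4 refers participants to examiners "who will not know the treatment group of the patient". Section 2.5.3 measures expression on "RNA extracted from blinded samples (ie. concealment of group allocation) to eliminate bias". The sealed envelopes in section 2.2 conceal the allocation sequence; they do not keep an arm hidden once treatment starts.

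Section 2.3 describes the arms:

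- All sessions are "led in person by well-educated, experienced therapists specially trained in each method".
- In the ICF arm, "The interdisciplinary team together with the patient will use the functional profile to define in detail the overall goal and sub-goals".
- The TECH arm uses exoskeleton robots or a virtual environment. The NEFI arm uses Vojta and Bobath therapy.
- For the control, "A comparative group will undergo standardly provided care at department of neurology". No sham or attention-matched control is described.

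Section 2.5.1 labels PROMIS as self-report. The short-term GAS goals are "evaluated by the rehabilitation team together with the rehabilitant". The mid-term and long-term goals are rated in a telephone interview. For WHODAS 2.0 the section does not say who answers; Table 2 lists it under the psychologist. The Introduction explains that the primary outcomes were chosen because patients' own sense of improvement was considered most important.

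**The concern.** A reader who sees double blinded will normally assume that the patient, and often the care provider, does not know the arm. That assumption matters most for subjective outcomes, and here all three primary outcomes are wholly or largely of that kind. A blinded examiner who reads out a questionnaire cannot mask the person answering it.

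The exposure is sharpest for hypothesis II in section 2.8, which predicts that ICF will do best on GAS, PROMIS and WHODAS. Goal setting with the patient is the ICF intervention itself, and the short-term GAS goals are then scored by the rehabilitation team with that patient. If knowledge of the arm moves the answers, a difference can appear without any treatment effect, and the label would tell readers that this had been excluded.

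**Working it through.** **Step 1. Who is masked, according to the text.**

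| Party or outcome | What the document supports | Where |
|---|---|---|
| Study examiners | Masked, stated | 2.4 |
| lncRNA samples | Masked, stated | 2.5.3 |
| Therapists | Deliver a named method in person; cannot be masked | 2.3 |
| Patients | Help set goals, use devices, receive hands-on therapy, or stay in ward care; no masking described | 2.3 |
| PROMIS | Self-report by the patient | 2.5.1 |
| GAS, short-term goals | Rehabilitation team with the patient | 2.5.1 |
| GAS, mid- and long-term goals | Telephone interview | 2.5.1 |
| WHODAS 2.0 | Respondent not stated; dependence on the patient's answers is inferred from the Introduction and the telephone follow-up | 2.5.1, Table 2, 2.4 |
| FIM, Berg Balance | Independent physical therapist; baseline and 3 weeks only | 2.5.2, Table 2 |

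That patients and therapists know the arm is an inference from these descriptions, not a statement in the protocol. I see no other reading that fits them.

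**Step 2. What a reporting shift would do to the planned test.** The documents give no figure for such a bias, so this is illustration only.

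Inputs:

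- Total 210 (2.6), allocated 1:1:1:1 (2.2): 210/4 = 52.5 per arm.
- Section 2.9 compares ICF with all other participants, one-sided. I take this as the other three arms: 3 × 52.5 = 157.5.
- α = .05 from section 2.6, applied to the one-sided test (assumption), so z = 1.645.
- Shift b = 0.1 or 0.2 SD in favour of the affected arms (assumption); no true effect.

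Standard error in SD units: √(1/52.5 + 1/157.5) = 0.1594.

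False-positive rate = Φ(net shift / 0.1594 − 1.645).

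*Only ICF shifted (net shift = b).*

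- b = 0.1: Φ(0.627 − 1.645) = 15.4%
- b = 0.2: Φ(1.255 − 1.645) = 34.8%

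*All three programmes shifted equally.* Two of the three comparison arms carry the same shift, so the net shift is b − 2b/3 = b/3.

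- b = 0.1: Φ(0.209 − 1.645) = 7.6%
- b = 0.2: Φ(0.418 − 1.645) = 11.0%

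**Step 3. Sensitivity to arm size.** Section 2.6 also states 70 per group, which over four arms would be 280 rather than 210. With 70 against 210, the standard error is √(1/70 + 1/210) = 0.1380. The rates become 17.9% and 42.2% if only ICF is shifted. With the b/3 shift they are Φ(0.242 − 1.645) = 8.0% and Φ(0.483 − 1.645) = 12.3%. The picture does not change.

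**The case against.** The strongest reply is that some masking is real. Examiners and laboratory samples are both stated to be blinded, and the protocol never says that *double* means patient and therapist. Blinding patients to a rehabilitation programme is rarely feasible, so its absence is no failure of conduct. This stands: the trial is not wholly open, and examiner-rated secondary outcomes keep some protection. It does not rescue the label. An undefined term will be read in its usual sense, and masking the examiner and the laboratory does not protect outcomes that rest on the patient's or the team's judgement.

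Several stronger readings are tempting, and the documents do not support them:

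- *That all primary outcomes are scored by the treating team.* This is stated only for the short-term GAS goals.
- *That WHODAS is declared to be self-report.* Only PROMIS is; for WHODAS it is an inference.
- *That a programme-versus-Group 4 comparison would be falsely positive 13-27% of the time.* With b = 0.1 and 0.2 and 52 per arm, Φ(b√26 − 1.645) does give .13 and .27. But section 2.9 specifies no one-sided two-sample test against Group 4. Hypothesis I has paired tests within each group, and comparison with control comes through the mixed model's F tests or the ANOVA and Tukey comparisons.
- *That the follow-up call unmasks the interviewer.* Section 2.3 says information "as to the health and social care the rehabilitant received after hospitalisation will be collected by phone call", and section 2.4 provides a telephone follow-up interview. Neither says that these are one call or one caller.
- *That agreement with FIM and Berg Balance would make the subjective contrasts blinded.* It would support them, but they stay unblinded whatever the other outcomes show.

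Nor should examiner masking be taken as fully secure. Section 2.4 lets specialists consult the hospital information system, and no safeguard against unmasking is described.

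**Conclusion.** The concern holds in this form: the double-blind label in the title and section 2.1 is not supported by the design described. Masking covers the examiners and the lncRNA samples. PROMIS and GAS depend on parties who are not masked, and WHODAS appears to. Between-group differences on these outcomes are therefore not double-blind evidence.

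That conclusion rests on the text and needs no arithmetic. The size of the consequence cannot be derived from the documents. Under an assumed shift of 0.1 to 0.2 SD, the nominal 5% one-sided error of the ICF-versus-rest test rises to about 8-11% or about 15-35%, depending on whether all three programmes or only ICF are affected. If awareness does not affect reporting, the error stays at 5%. The trial remains worth running; what changes is what its primary comparisons can be said to show.

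**What to change.** - In the title and section 2.1, replace double blinded with assessor-blinded (examiners and laboratory).
- In section 2.5, state for each outcome who answers, who scores and who is masked. Say explicitly who answers WHODAS 2.0.
- In section 2.9, describe every between-group contrast on PROMIS, WHODAS and GAS as unblinded, whatever the other outcomes show.
- Report the 3-week contrasts beside FIM and Berg Balance, which are examiner-rated and already collected then. Note that no examiner-rated comparator exists at 3 and 12 months, where hypothesis II expects the largest ICF benefit on the primary outcomes.
- If outcome questions and questions about care received are asked in the same call, ask the outcome questions first.

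The cost is wording, question order and the loss of a favourable label. No new patients, visits or measures are needed. These changes do not alter who scores GAS; they make it visible to the reader.
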